### 6.11.2 Laboratory Data

Descriptive statistics of the observed values and change from baseline (continuous data) will be presented by treatment group and visit for each hematology, serum chemistry, coagulation and urinalysis parameter. Change from baseline in categorical parameters will be presented in the natural order of the outcome where possible.

Each measurement (for continuous data and for categorical data where provided) will be classed as below, within, or above normal range, based on ranges supplied by the laboratory used. Shift tables in relation to the normal range from baseline to each follow-up visit will be presented.

All individual laboratory data, including serology, drug, alcohol and cotinine screening, pregnancy testing and FSH data will be listed, with a separate listing of any clinically significant laboratory measurements recorded throughout the study presented in Appendix 14.3.4 of the CSR.

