3.2 Stopping Rules for Cohorts for Participants Receiving Active Drug

If any of the cohort stopping rules are met, cohort dosing must be stopped to allow review of the data by the Sponsor and the Investigator. As with dose escalation review, the review of data here is also blinded except for review by the 2 experienced

individuals not directly involved in the study (see unblinding procedures; Section 6.2.6).

Rules for stopping dosing of a cohort include the following:

- a. One subject experiences one or more drug-related SAEs.
- b. Two or more subjects experience Grade 3 or 4 (per DMID) myalgia in combination with increase of CPK (at least 3 times the upper limit of the normal range [ULN] confirmed at 48 hours).
- c. Two or more subjects have a QTcF \geq 500 ms with an increase from baseline > 60 ms.
- d. Two or more subjects experience confirmed Grade 3 or 4 AEs (per DMID) in any one of the following laboratory parameters: alanine aminotransferase (ALT), aspartate aminotransferase (AST), alkaline phosphatase (ALP), amylase, or lipase.

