For Cohort 7, a total of 124 mL (31 x 4 mL samples) will be collected from each subject for PK analysis. Approximately 78.5 mL of blood will be collected for the clinical laboratory evaluations and coagulation testing. The total volume of blood collected from each subject in Part 1 Cohort 7 will not exceed approximately 203 mL.

6.7.2 Part 2

A total of 212 mL (53 x 4 mL samples) will be collected from each subject for PK analysis. Approximately 110.6 mL of blood will be collected for the clinical laboratory evaluations and coagulation testing. The total volume of blood collected from each subject in Part 2 is planned not to exceed approximately 322.6 mL, although more may be collected if a decision is made to prolong PK monitoring.

Table 9 Total Volume of Blood to be Collected for Testing: Part 2

Reason for Collection	Number of Samples	Volume per Sample (mL)	Total Volume (mL)
Clinical labs at screening	1	12.5	12.5
Clinical labs during study (check-in, Days 7, 14, 21, 42, 63, 84, 105, and 126 (end-of-study)	9	8.5	76.5
Coagulation	8	2.7	21.6
Pharmacokinetic analysis (predose trough)	13	4.0	52.0
Pharmacokinetic analysis (postdose)	40	4.0	160.0
		Total	322.6

Additional PK samples may be collected at times to be determined based on the results from previous cohorts.

The Principal Investigator, in conjunction with the Sponsor, may collect additional blood if necessary, for repeat laboratory or safety evaluations including AE follow-up.

6.7.3 Part 3

A total of 128 mL (32 x 4ml samples) will be collected for PK Analysis. Approximately 91 mL of blood will be collected for the clinical laboratory evaluations and coagulation testing.

Table 10 Total Volume of Blood to be Collected for Testing: Part 3

Reason for Collection	Number of Samples	Volume per Sample (mL)	Total Volume (mL)
Clinical labs at screening	1	12.5	12.5
Clinical labs during study (check-in, 6 and 48 hours and Days 5, 7, 10, and 14 (end-of-study).	7	8.5	59.5
Coagulation	7	2.7	18.9
Pharmacokinetic analysis	32	4.0	128.0
		Total	218.9

The Principal Investigator, in conjunction with the Sponsor, may collect additional blood if necessary, for repeat laboratory or safety evaluations including AE follow-up.

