## 6 PLANNED ANALYSES

No statistical analysis plan (SAP) prepared in advance of the data can be definitive and the final Clinical Study Report (CSR) may contain additional tables or statistical tests if warranted by the data obtained. The justification for any such additional analyses will be fully documented in the final CSR.

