## 6.2.3 Baseline

Baseline is defined as the last non-missing value (either scheduled, unscheduled or repeat) before the subject receives the first (or single) dose of study drug in the relevant study part.

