## 6.2.4 Early Withdrawal Assessments

Early withdrawal assessments will be tabulated with End of Study (EOS).

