## 6.2.10 Unscheduled Visits

Only scheduled post-baseline assessment values will be tabulated. Post-baseline repeat / unscheduled assessments will not be summarized, but these post-baseline assessments will be listed in the relevant appendices to the CSR.

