14.3.2.1.1	TEAEs Leading to Early Discontinuation from Study, Listing – Safety Analysis Set	IP	
14.3.2.1.2	TEAEs Leading to Withdrawal of Study Drug, Listing – Safety Analysis Set		
14.3.2.2	Serious TEAEs, Listing – Safety Analysis Set	IP	
14.3.2.3	Deaths, Listing – Safety Analysis Set	IP	
14.3.3	Narratives of Deaths, Other Serious, and Certain Other Significant Adverse Events		
	Placeholder for Medical Writing		
14.3.4	Abnormal Laboratory Values		
14.3.4.1	Laboratory, Listing of Clinically Significant Values – Safety Analysis Set	IP	
14.3.5	Extent of Exposure, Dosage Information, And Compliance		
14.3.5.1	Extent of Exposure – Safety Analysis Set	IP	
14.3.6	Vital Signs and Physical Examination		
14.3.6.1	Vital Signs, Descriptive Statistics – Safety Analysis Set	IP	
14.3.6.2	Physical Examination, Descriptive Statistics – Safety Analysis Set	IP	
14.3.6.3	Heart Murmur Examination, Descriptive Statistics – Safety Analysis Set	IP	
14.3.7	Other Safety		
14.3.7.1	Hematology Data, Descriptive Statistics – Safety Analysis Set	IP	
14.3.7.2	Hematology Data, Normal Range Shifts – Safety Analysis Set	IP	
14.3.7.3	Serum Chemistry Data, Descriptive Statistics – Safety Analysis Set	IP	14.3.7.1
14.3.7.4	Serum Chemistry Data, Normal Range Shifts – Safety Analysis Set	IP	14.3.7.2
14.3.7.5	Coagulation Data, Descriptive Statistics – Safety Analysis Set	IP	14.3.7.1
14.3.7.6	Coagulation Data, Normal Range Shifts – Safety Analysis Set	IP	14.3.7.2
14.3.7.7	Urinalysis Data, Descriptive Statistics – Safety Analysis Set	IP	
14.3.7.8	Urinalysis Data, Normal Range Shifts – Safety Analysis Set	IP	14.3.7.2
14.3.7.9	12-Lead ECG Data, Descriptive Statistics – Safety Analysis Set	IP	
14.3.7.10	12-Lead ECG Data, Overall Interpretation – Safety Analysis Set	IP	
14.3.8	Concomitant Medication		
	Not Applicable		
14.4	PK Tables		
14.4.1.1	Descriptive Statistics for Concentration-Time Data of TBAJ-876, M2, and M3 after Single Doses of 10 mg (Cohort 1), 25 mg (Cohort 2), 50 mg (Cohort 3), 100 mg (Cohort 4), 200 mg (Cohort 5), 400 mg (Cohort	IP	

QMD Ref: Worldwide-TMP-ST-006-4.0 Effective: 12Aug2019

Governing QMD: Worldwide-SOP-ST-001

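### No planned laboratory table counts subjects by worst post-baseline CPK, and in Part 2 a 48-hour repeat or symptom-driven CPK will usually be found in listings only

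*SAP*

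**What the plan says.** SAP 6.11.2 plans two displays for each laboratory parameter: descriptive statistics by treatment group and visit, for observed values and changes, and shift tables from baseline to each later visit. For the shifts each measurement "will be classed as below, within, or above normal range". SAP 6.3 limits the descriptive statistics to n, mean, median, SD, minimum and maximum. The list in SAP 9 confirms that serum chemistry has two tables, 14.3.7.3 (descriptive statistics) and 14.3.7.4 ("Serum Chemistry Data, Normal Range Shifts"). Output 14.3.4.1 is a listing of clinically significant values, not a count.

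SAP 6.2.10 adds: "Post-baseline repeat / unscheduled assessments will not be summarized". Those values go to listings. The baseline rule in SAP 6.2.3 is wider: "Baseline is defined as the last non-missing value (either scheduled, unscheduled or repeat"). One off-schedule route into the tables exists, in SAP 6.2.4: "Early withdrawal assessments will be tabulated with End of Study (EOS").

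The protocol uses two CPK levels. Exclusion criterion 9 in section 5.2 bars entry above 1.25 x ULN. Stopping rule b in section 3.2 needs two or more subjects with Grade 3 or 4 myalgia together with an "increase of CPK (at least 3 times the upper limit of the normal range [ULN] confirmed at 48 hours"). Part 2 blood draws are set out in Protocol 6.7.2, Table 9: "Clinical labs during study (check-in, Days 7, 14, 21, 42, 63, 84, 105, and 126 (end-of-study").

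**The concern.** Protocol 1.3 names skeletal muscle damage, with diarrhea, as what limited the dose in the 13-week rat study, and reports very high serum CK alongside it. Protocol 1.6 asks for this risk to be followed through chemistry biomarkers and through muscle pain or weakness. The natural safety question is therefore how many subjects at each dose, against placebo, had a marked CPK rise at any time after dosing.

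The planned laboratory tables do not answer it. They do not separate small from large rises, they do not take the worst value in a subject, and they leave out the samples most likely to be drawn because of symptoms or to confirm a high result. A report could then describe CPK on the primary objective without a count at the one post-dose level that the protocol itself uses.

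**Working it through.** The plan states no figure to reproduce. The check sets its rules against the protocol's CPK level and lab schedule.

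**1. What the shift classes can show.** There are three classes. Illustrative values of 1.1, 3 and 30 x ULN all fall in the top one. Entry is allowed up to 1.25 x ULN, so a subject moving from 1.2 to 20 x ULN (also illustrative) reads as above to above. The 3 x ULN level cannot be read from any cell.

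**2. What the descriptive table can show.** The maximum at each scheduled visit would reveal a single large scheduled value. It would not say how many subjects passed 3 x ULN, or link two values in one subject.

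**3. Part 2 lab spacing** (Protocol 6.7.2, Table 9; Table 16).
- Post-dose labs: Days 7, 14, 21, 42, 63, 84, 105, 126.
- Gaps: 7, 7, 21, 21, 21, 21 and 21 days. The smallest is 7 days = 168 hours, so no two scheduled draws are 48 hours apart.
- Hence, for any Part 2 rise confirmed at 48 hours, at least one of the two values is untabulated. The exception is an early-withdrawal sample that happens to fall 48 hours from the other one.
- Dosing days without a scheduled lab: Days 1 to 6 and 8 to 13 = 6 + 6 = 12 of 14. Over confinement Days 1 to 21, 21 - 3 = 18 of 21 have none.
- From only two of those 12 dosing days (5 and 12) does a 48-hour repeat land on a scheduled day (7 and 14). The first value is then the one left out.

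**4. Parts 1 and 3** (Protocol Tables 15 and 17, footnote e; Day d taken as (d - 1) x 24 hours).
- Both schedules include 6 hours, 48 hours, Day 5 (96 hours) and Day 7 (144 hours).
- 96 - 48 = 48 and 144 - 96 = 48, so two scheduled 48-hour pairs exist. No later visit adds one.
- The protocol gives no window for the 48 hours. Allowing +/- 6 hours would add the 6-to-48-hour pair (42 hours). Part 2 would still have none.
- Even where both values are tabulated, by-visit tables do not join them within a subject.

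**5. Whether adverse event grading supplies the count.** Protocol 7.7 makes every laboratory change of Grade 2 or more an adverse event. The enzyme rows in Protocol Appendix 3 are AST, ALT, GGT, alkaline phosphatase, amylase and lipase. CPK has no row, so it falls to the generic scale, which grades by discomfort, activity limits and need for treatment. The grade of a CPK event therefore does not measure the size of the rise.

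**The case against.** Much of the muscle signal is reported elsewhere, and this stands.
- Myalgia and muscle strength have graded DMID rows, and treatment-emergent events are tabulated by dose and maximum grade (Table 14.3.1.4).
- The rat finding also came with high AST and ALT. Both have DMID rows, so Grade 2 rises must be reported as adverse events.
- A CPK change judged clinically significant must be reported as an adverse event (Protocol 7.7). Adverse event tables are not tied to visits, so an unscheduled value can reach a table that way.
- Listing 14.3.4.1 covers clinically significant values throughout the study. Active groups of 6, 9 or 10 subjects are small enough to count by hand.
- No protocol text promises a worst-value table, and SAP 6 says the study report "may contain additional tables or statistical tests if warranted by the data obtained".

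What remains is that the CPK adverse event and Listing 14.3.4.1 both depend on the investigator's judgement of significance. Neither gives a count at 3 x ULN.

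A reader might infer four stronger things that the documents do not support.
- **That subjects were less protected, or stopping rule b could not be applied.** Protocol 3.1, 3.2 and 6.2.6 run escalation and stopping on data reviewed during the study, including unblinded review by two people outside it. These tables are for the study report.
- **That CPK of 3 x ULN is itself a stopping criterion.** Rule b also needs Grade 3 or 4 myalgia, in at least two subjects.
- **That a table added later would need cut-offs invented after seeing data.** The 1.25 and 3 x ULN levels are already in the protocol.
- **That the lab spacing gives a probability of missing a rise.** It shows only which values the rule can tabulate.

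**Conclusion.** The point holds as a modest reporting weakness on the primary safety objective, not an error in conduct. SAP 6.11.2 and 6.2.10 together leave no planned laboratory table with the number of subjects per dose and on placebo whose worst post-baseline CPK reached 3 x ULN. The effect is clearest in Part 2, where no scheduled pair of labs can hold both a first value and its 48-hour confirmation.

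This rests on three assumptions: that the Part 2 lab days stay as printed (Protocol 3 allows the safety schedule to be revised), that confirmation at 48 hours means a second sample about 48 hours later, and that SAP 6.2.10 is applied literally. Nothing is lost from the data, because every value remains in listings. How many subjects would be affected cannot be estimated from the documents.

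**What to change.** Add one CPK table to SAP 6.11.2 and SAP 9, stated as an exception to 6.2.10: baseline against worst post-baseline value, counting scheduled, repeat and unscheduled samples, in multiples of ULN.
- **Bands:** <=1, >1 to 1.25, >1.25 to <3, and >=3, using the protocol's own cuts.
- **Columns:** each dose and pooled placebo in Part 1 and in Part 2. Part 3 has no placebo, so show its three groups.
- **Flags:** subjects with >=3 x ULN confirmed at about 48 hours, with the window written down, and separately those who also had Grade 3 or 4 myalgia, so that the table lines up with stopping rule b.
- **Footnote:** unscheduled draws may be more frequent in subjects with symptoms, so the chance of catching a high value may differ between subjects and groups.

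The cost is a short SAP edit and one extra table. CPK values, repeats and laboratory ranges are already collected, so no sampling changes.

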### 6.11.3 Vital Signs

Descriptive statistics for observed values and changes from baseline in the following vital signs will be presented by treatment group at each visit:

- Systolic blood pressure (mmHg)
- Diastolic blood pressure (mmHg)
- Pulse rate (bpm)
- Respiration rate (breath/min)
- Body temperature (degrees Celsius)
- Pulse oximetry (%)

All vital sign data (including body weight at screening) will be listed.

QMD Ref: Worldwide-TMP-ST-006-4.0 Effective: 12Aug2019	Governing QMD: Worldwide-SOP-ST-001
Confidentiality Statement	

This document is the property of Worldwide Clinical Trials Inc. and may not be duplicated, copied, altered or removed from company without prior approval from Worldwide Quality Assurance or in compliance with Worldwide Standard Operating Procedures.

Worldwide Clinical Trials Controlled Quality Management Document		
 WORLDWIDE CLINICAL TRIALS	Sponsor:	Global Alliance for TB Drug Development
	Protocol Number:	TBAJ-876-CL001
STATISTICAL ANALYSIS PLAN – PHASE 1		

#### 6.11.4 Physical Examination

Shift tables for the observed status of each of the body systems, i.e., Normal, Abnormal NCS (Not Clinically Significant), and Abnormal CS (Clinically Significant) from baseline to each follow-up visit will be tabulated by treatment group. All data, including details of clinically significant findings will be listed.

#### 6.11.5 Heart Murmur Examination

Shift tables for the presence of heart murmur (Not Present, Present NCS, and Present CS) from baseline to each follow-up visit will be tabulated by treatment group. All data, including details of clinically significant findings will be listed.

#### 6.11.6 Electrocardiogram Data

Descriptive statistics for observed values and changes from baseline in the following ECG variables will be tabulated by treatment group at each visit:

- Heart rate (bpm)
- PR duration (ms)
- QRS duration (ms)
- RR interval (ms)
- QT interval (ms)
- QTc interval (ms)
- QTcB interval (ms) [Bazett's formula]
- QTcF interval (ms) [Fridericia's formula]

Shift tables in relation to the overall interpretation (Normal, Abnormal NCS, and Abnormal CS), from baseline to each follow-up visit will be presented. All ECG data, including details of any abnormalities, will be listed.

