6.9.5 Electrocardiograms

For Part 1, triplicate ECGs will be completed at screening, Day -1, 48 hours, and Day 8 or early withdrawal only. All other time points will be single ECG readings within 15 minutes of time points on Table 15.

The predose ECG will be performed prior to the predose blood draw. If a subject experiences a postdose QTcF >500 msec or a change from baseline QTcF >60 msec, after repeat testing, additional ECGs should be recorded until normalization or return to baseline.

For Cohort 7, all ECGs will be triplicate at each time point. In addition, subjects in will have triplicate ECGs at 16 hours postdose.

For Part 2, triplicate ECGs will be completed at screening, Day -1, Day 15 or early withdrawal only. All other time points on Table 16 will be single ECG readings. ECGs

may be done within 2 hours prior to time of dosing and at 6 hours after dosing on Days 1, 2, 3, 8, 12, 14, and on Days 42, 63, 84, 105, and 126.

For Cohorts 2 and 3, an additional ECG extraction will occur at 16 hours postdose on Day 1 and Day 14. For Cohort 3, all ECGs performed will be triplicate ECGs at each time point listed in Table 16.

For Part 3, triplicate ECGs will be completed with 15 minutes at all timepoints on Table 17.

NOTE: Where possible, ECG extractions should be taken from the continuous 12-lead ECGs (Holter).

The predose ECG should be completed within 1 hour prior to the predose blood draw. If a subject experiences a postdose QTcF >500 ms with a change from baseline QTcF >60 ms, after repeat testing, the Principal Investigator should be notified, and additional ECGs should be recorded until normalization or return to baseline.

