- timepoints as noted in above flow chart. If a subject experiences a postdose QTcF >500 msec or a change-from-baseline QTcF >60 msec, after repeat testing, additional ECGs will be recorded until normalization or return to baseline. All ECGs in Cohort 7 will be triplicate at each time point. In addition, subjects in Cohort 7 will have triplicate ECGs at 16 hours postdose.
- e. Safety laboratory assessments will be done at check-in (Day -1), 6 and 48 hours postdose and on Days 5, 7, 10, 14, 17, 21, and 28. The following analyses will be performed:
 - Full blood cell count (hemoglobin, hematocrit, red blood cell count, white blood cell count with differential, reticulocyte count, platelet count), reticulocyte count
 - Coagulation Tests: Activated partial thromboplastin time (aPTT2), Prothrombin time (PT2)
 - Clinical Chemistry (albumin, serum urea, creatinine, direct, indirect, and total bilirubin, uric acid, total protein, alkaline phosphatase, aspartate aminotransferase (AST), alanine aminotransferase (ALT), phosphate, sodium, potassium, calcium (corrected for albumin), chloride, magnesium, glucose, bicarbonate/CO2, creatine phosphokinase (CPK), creatine phosphokinase myocardial band (CPK-MB), lipase, and amylase
 - Other laboratory tests: cardiac troponin I and glycosylated hemoglobin
 - Urinalysis (pH, specific gravity, protein, glucose, micro-albumin, ketones, bilirubin, creatinine, nitrite, sodium, urobilinogen, myoglobin, blood, leukocytes). If protein, occult blood, nitrite, or leukocyte esterase values are out of range, a microscopic examination will be performed. Myoglobin will be collected but results will not be required for dose qualification.
- f. Female subjects will have a urine pregnancy test at the end-of-study on Day 28 or early withdrawal.
- g. Subjects will be monitored from the time of signing the informed consent and throughout the study via safety assessments, observation and subject reporting. A specific inquiry regarding AEs will be conducted prior to dosing and at time points specified postdose and upon return to clinic for subsequent visits.
- h. TBAJ-876 or Placebo for TBAJ-876 Oral Suspension will be administered orally followed by 240 mL of water. Listerine® strips will be used as a blinding agent. A strip will be added to the subject's tongue before and after each dose.

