## 6.2.9 Electrocardiogram Data

For ECG data recorded on continuous scales, if more than one value is recorded at a time point, the mean value rounded to the integer will be presented. For overall interpretation if more than one value is recorded, the most severe (worst case) of the respective readings will be taken.

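### Once a QTcF limit is crossed, the SAP's safety-ECG tables do not show how many subjects crossed it, and they omit any higher value seen only on a repeat or unscheduled ECG

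*SAP*

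**What the plan says.** **Tables planned.** SAP 6.11.6 states: "Descriptive statistics for observed values and changes from baseline in the following ECG variables will be tabulated by treatment group at each visit". QTcF is one of the eight variables it names. SAP 6.3 defines the statistics for a continuous variable as n, mean, median, SD, minimum and maximum. SAP 6.11.6 adds shift tables for the reader's overall interpretation (normal, or abnormal with or without clinical significance). The output list in SAP 9 has two ECG tables to match: 14.3.7.9, "12-Lead ECG Data, Descriptive Statistics", and 14.3.7.10 for the interpretation. Neither counts subjects against a QTcF limit.

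**ECGs that enter the tables.** SAP 6.2.10 admits only scheduled post-baseline values: "Post-baseline repeat / unscheduled assessments will not be summarized", although they are listed. For several readings at one time point, SAP 6.2.9 says "if more than one value is recorded at a time point, the mean value rounded to the integer will be presented". All ECG data go into listing 16.2.8.8.

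**Limits the protocol uses.** Stopping rule (c) in Protocol 3.2 needs two or more subjects with QTcF of at least 500 "ms with an increase from baseline > 60 ms". Protocol 6.9.5 words the trigger for extra ECGs in two ways. The Part 1 text has "a postdose QTcF >500 msec or a change from baseline QTcF >60 msec", and the end of the section has "a postdose QTcF >500 ms with a change from baseline QTcF >60 ms". The footnotes to Tables 15 to 17 use the *or* form. Footnote d of Table 15 continues: "after repeat testing, additional ECGs will be recorded until normalization or return to baseline".

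**The concern.** The protocol's QT stopping criterion counts subjects and requires two conditions in the same subject. The SAP's tables describe each visit separately and treat QTcF and its change as separate variables, so they do not carry the information the criterion needs. The ECGs left out by SAP 6.2.10 include those the protocol orders around a QT crossing. Baseline is handled differently: SAP 6.2.3 allows it to come from an unscheduled or repeat value.

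Safety is the primary objective. Protocol 1.6 lists QTc prolongation among the effects of the similar marketed drug, although Protocol 1.2 expects a low risk for this compound. Protocol 6.9.6 says the ECG analysis will concentrate on QT and refers to the SAP for the details. What is at stake is how clearly the study report shows, by dose and against placebo, how many subjects crossed a limit and how high they went.

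**Working it through.** The documents give no figure on this point, so there is none to reproduce. The values below are constructed to show what the tables can and cannot tell apart. They are not trial data and not a forecast.

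**1. What the tables do settle.** Take the largest of the per-visit maxima. If it is below 500 ms for QTcF, no subject has a scheduled value ≥500 ms. If it is at most +60 ms for the change, no subject has a scheduled increase >60 ms. In both cases the scheduled count is exactly zero. If a maximum crosses a limit, at least one subject did.

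**2. How many subjects.** Inputs: 9 active subjects (MAD cohort, Protocol 6.1) and the ECGs 6 hours after dosing on Days 8, 12 and 14 (Protocol 6.9.5). Assumed baselines are 420 ms for subjects 1 to 3, and 400, 405, 410, 415, 425 and 430 for subjects 4 to 9. Subjects 4 to 9 change by 0, 5, 10, 15, 20 and 25 ms at every visit. Subjects 1 to 3 change as follows:

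| Version | Day 8 | Day 12 | Day 14 | Subjects with any increase >60 ms |
|---|---|---|---|---|
| A | 65, 40, 30 | 65, 40, 30 | 65, 40, 30 | 1 of 9 |
| B | 65, 40, 30 | 30, 65, 40 | 40, 30, 65 | 3 of 9 |

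At every visit, in both versions:

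- QTcF values: 400, 410, 420, 430, 445, 450, 455, 460, 485. Sum 3955, mean 3955/9 = 439.4, median 445, SD 26.86, range 400 to 485.
- Changes: 0, 5, 10, 15, 20, 25, 30, 40, 65. Sum 210, mean 210/9 = 23.3, median 20, SD 20.00, range 0 to +65.

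The tables are identical, but the counts are 1 and 3. With 6 active subjects (SAD size: subjects 1 to 3 plus baselines 400, 410, 430 with changes 0, 10, 25), the counts are again 1 and 3.

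The same happens at rule (c)'s own criterion. Take 9 subjects, all with baseline 420, and values 505, 440, 438, 436, 434, 432, 430, 428, 426 at each of two visits (mean 3969/9 = 441, SD 24.43, maximum 505, largest change +85). If the 505 belongs to one subject both times, 1 of 9 (11.1%) meets the criterion. If it belongs to a different subject each time, 2 of 9 (22.2%) do.

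**3. Whether both limits fall in one subject.** Take three subjects at one visit, with baselines 450, 437 and 400 in both cases.

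| Baseline | Case X | Case Y |
|---|---|---|
| 450 | 502 (+52) | 465 (+15) |
| 437 | 452 (+15) | 502 (+65) |
| 400 | 465 (+65) | 452 (+52) |

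Both cases have QTcF values 452, 465, 502 and changes +15, +52, +65, so both give the same table. In X, no subject has QTcF ≥500 ms together with an increase >60 ms. In Y, one does.

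**4. A peak on a repeat.** One subject has baseline 420, a scheduled value of 490 (490 − 420 = +70) and a repeat of 505 (505 − 420 = +85). All other subjects are lower. The tables show maxima of 490 and +70. The count with QTcF ≥500 ms is 0 from scheduled ECGs and 1 from all ECGs. The table does show that +60 was crossed, but not that 500 was reached. Extra ECGs after 490 (+70) follow from the *or* trigger. Under the *with* wording, that value would not by itself order them.

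**The case against.** The strongest reply is that the tables already give enough. Per-visit maxima prove a scheduled count of zero in the expected case: low QT risk, with entry capped at QTcF 450 ms for men and 470 ms for women. Where a scheduled value triggers extra ECGs, that value is itself tabulated, so the signal is not hidden. With 6 or 9 active subjects per cohort, counting from the listing takes minutes. The study is not formally powered, no protocol text promises a table of threshold counts, and keeping repeats out of summaries is a general rule that avoids favouring subjects who are measured more often. All of this stands, and it limits the size of the point. It does not supply the head-count, the joint criterion or the height of a repeat.

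Adverse event reporting does not clearly fill the gap either. The rules that make a finding an AE (Protocol 7.2 and 7.7) cover laboratory changes and blood pressure findings of Grade 2 or above. A QTcF crossing is left to the investigator's judgment.

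A reader might infer more than the documents support:

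- *A cohort stop could be missed.* Rule (c) is applied during the study, with dosing halted for review and unblinded review by two people outside the study (Protocol 3.1, 3.2). It does not rest on report tables.
- *The cut-offs would be chosen after seeing the data.* SAP 6 does allow extra tables in the report, but 500 and 60 ms are already in the protocol. What stays open is > or ≥ at exactly 500, and which ECGs count.
- *SAP 6.2.9 would average a repeat with the first reading.* SAP 6.2.10 governs repeats explicitly. SAP 6.2.9 also takes the worst reading for overall interpretation.
- *No QT threshold analysis exists anywhere.* Protocol 6.2.5 and Appendix 4 give ECG reading and aggregate presentation to a cardiac vendor. SAP 6.11.7 lists only Holter start and stop data, so the vendor's output cannot be judged from these documents.

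**Conclusion.** The point holds as a limited one: a gap in this SAP's summary tables, worth closing because it is cheap. When no limit is crossed on a scheduled ECG, the tables give the scheduled count correctly. When one is crossed, the same tables can fit 1 or 3 of 9 subjects above +60 ms, and 1 or 2 of 9 meeting both parts of rule (c). They also cannot place the two parts in the same subject, and a value found only on a repeat or unscheduled ECG appears in listing 16.2.8.8 but in no table.

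These sizes come from constructed values with assumed baselines. They show what is possible, not what is likely. The conclusion also assumes that repeat and additional ECGs are recorded as repeat or unscheduled assessments, so that SAP 6.2.10 applies to them.

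**What to change.** Add one table to SAP 6.11.6, by dose and pooled placebo within Parts 1 and 2, and by group in Part 3, which has no placebo. It gives the number of subjects with:

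- any post-dose QTcF ≥500 ms;
- any increase from baseline >60 ms;
- both at the same time point.

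These are the cut-offs of stopping rule (c). State them explicitly, because the trigger in Protocol 6.9.5 uses >500.

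In SAP 6.2.10, say that this table includes scheduled, repeat and unscheduled ECGs, that replicates of one recording are averaged as in SAP 6.2.9, and that each repeat counts as its own ECG. Show the scheduled-only count beside it.

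The cost is one table and a few lines of SAP text, from data already collected and listed. The drawback is that subjects who trigger extra ECGs have more chances to cross a limit. The scheduled-only column makes that visible. No trial decision changes.
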